7.2.1 Packaging and Labelling

The Neurotech Vital Compact device will be provided packaged, along with its electrode lead and hydrogel electrodes, in a box with an identifying serial number, part number and subject number. The device will also bear the CE mark.

The Neurotech Vital garments will be separately packaged and also will have their own identifiable lot numbers. Expiry dates will also be found on the electrode packaging.

The itouch Sure Pelvic Floor Exerciser will be provided packaged, along with vaginal lubricating gel, in a box with identifying serial number and subject number. The device will bear the CE mark.

Each device will be in packaging with a label with at least the following information:

For Clinical Trial Use Only

Study Number: BMR-13-1001

Contents: One Neurotech Vital Compact or itouch Sure Pelvic Floor Exerciser

Subject Number: XXXXX

Treatment Duration: 12 weeks at 30 minutes 5 days a week (Neurotech Vital Compact) or 12 weeks of 20 minutes 7 days a week (itouch Sure Pelvic Floor Exerciser)

Lot number: XXXXXXXX

Storage: Store at ambient (room) temperature

Study Sponsor and Manufacturer for Neurotech Vital Compact: Bio-Medical Research Ltd., [name].

US Study Director Expedite Research, LLC, [name]

Caution: The Neurotech Vital Compact is an investigational device limited by US Federal Law to be used by qualified Investigators only.

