8.10.3 Treatment Programme Schedule – itouch Sure Pelvic Floor Exerciser

Subjects will be advised that they should empty their bladder prior to commencing the 20 minute session of the itouch Sure Pelvic Floor Exerciser at home.

In accordance with the instructions for use for the device, the subjects will be instructed to use the device at home once per day for the 12-week period. Each treatment cycle is fixed at 20 minutes and the device will alert the subject when the cycle is completed.

Subjects will be advised that during the 12-week treatment programme not to do any new pelvic floor exercises.

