8.11.4 One Week Prior to Visit

Approximately 7 days before each of the planned assessments, subjects will be contacted by telephone to remind them that their follow-up appointment is due and that they should start completing the 7-day voiding diary they have been provided which collects information on number of leaks and number of pads used per day. They will also be reminded that they should also start using their pre-packaged pads to complete the 24-hour pad collection 3 days prior to their appointment and remind them to bring the diary, pads and device back to the clinic.

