6. Remove the covers from the **black side** of the electrodes. Do not throw these covers away as you have to put them back on the electrodes at the end of the session. With the electrodes facing the body, wrap the right stress garment firmly around the right leg and fasten. Please refer to the separate **Quick Start Guide** for more detail. Then repeat the same steps, wrapping the left stress garment around the left leg and fasten.

Note:

- The whole surface of each electrode must be in contact with the skin to ensure a successful treatment.

7. When the garments are placed on the body, the electrodes should lie on the quadriceps, hamstrings and gluteal muscles of both legs as per Fig. 10, 11 and 12.

Note:

- Only use electrodes specified for use with Vital Compact.

Important

You should consult your clinician before using this device and ensure that you have been given full instructions on how to use it correctly.

RUNNING PROGRAM 1

1. Ensure the battery is sufficiently charged. If the battery charge is low, connect the charger to the unit (Fig. 13) and plug it into an electrical socket. You should charge the battery for approximately 5 hours. It is fully charged when all 5 bars of the battery symbol (████) on the display screen are visible.

Important:

Once the battery is fully charged, let the unit cool down for a couple of minutes as the battery heats-up during charging.

Warning: For all users, including those with Impaired sensory capabilities:

The controller should not be handled at any time during the charge cycle. If the charge cycle is terminated early, please do not handle the controller for at least 1 hour, as surfaces may be hot.

2. Ensure the electrodes and garments are positioned correctly.

3. Connect the stress lead to the connector socket on the controller (Fig. 14).

4. Connect the stress lead to the garments by inserting the **blue** plug on the **left** garment into the **blue** connector on the stress lead (Fig. 15) and the **red** plug on the **right** garment to the **red** connector on the stress lead (Fig. 16).

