Step 6: Lubricate the itouch sure Probe with the conductive gel provided.

Step 7: After the wires are securely connected, insert the Probe into the vagina, in the same way you would a tampon, until only the flange at the end is visible.
The Probe will naturally position itself with the widest part of the flange vertically (see diagram).

Note: The flange should not be inserted into the vagina and should remain outside of the vagina at all times.

It is important to relax and choose a comfortable position - such as a semi-reclined pose - or to lie down on a bed or couch when performing this step.

Step 8: Turn the itouch sure ON by pressing the ON button (↑) for three seconds. When the unit is switched ON an audible "beep" will be heard.

Step 9: You will be using the STRES program in this study. The P Button is used to change the program. Please do not change the Program. If you accidentally change it you can get the STRES program back again by pressing the P button a few times.

Step 10: After insertion, adjust the strength by pressing the strength (↗) button. The selected intensity will appear on the display. Begin to increase the strength to a level where you feel the sensation but is not overly painful. You may not feel any sensation until the strength reaches a certain level. This level may vary based on individual use and any pre-existing physical conditions, but stimulation occurs as soon as the strength is registered above 0.

Note: It is important to be conservative upon initial use. As long as you can feel the contraction, itouch sure is working. You can build up the strength slowly over a number of days.

During use you may feel cramping. If this happens, stop using the itouch sure until the cramping goes away, then start again using a lower strength.

Step 11: To decrease intensity, press the strength down (▼) button.

NOTE: itouch sure cycles between active stimulation and periods of rest to allow your muscles to recover between contractions. It is normal to feel the stimulation ramp down, stop briefly, and then ramp back up again during treatment. (During the "rest" period, the strength display flashes "0.0".)

Step 12: The length of each session has been set at 20 minutes. Please do not change the preset time.

Step 13: When the timer reaches zero, your session is complete. Press and release the OFF button once to turn off the power or it will automatically turn off.

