3.2 URINE LEAKAGE FROM 24-HOUR PAD WEIGHT TEST

The urine leakage from the 24-hour pad weight test is based on the increase in the weight of 8 pads (including packaging) after 24 hours of collection. If fewer than 8 pads are returned, the urine leakage can only be determined if the missing pads were unused; in this case, the return weight is adjusted by the weight of the missing pads (where the average weight of one single dry pad with packaging is 16.7 g).

The 24-hour pad weight test collects urine leakage across three consecutive 24-hour periods at each timepoint. The average of the 24-hour periods at each timepoint will be used for the analysis of this data.

3.3 7-DAY DIARY ENDPOINTS

The number of incontinence episodes (accidental leaks) and the number of pads used in each 24-hour period were to be collected for 7 days prior to Baseline and Weeks 4, 12, and 26. The analyses will be based on the average values from all entries in the 7 day period.

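### Lubricating gel from the itouch probe may be weighed as urine on the Week 4 and Week 12 24-hour pads, in one arm only, and no visible instruction or analysis addresses it

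*Protocol*

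**What the plan says.** **Gel in the comparator arm.** Protocol 7.2.1 states: "The itouch Sure Pelvic Floor Exerciser will be provided packaged, along with vaginal lubricating gel". Step 6 of the itouch instructions (Appendix XII) reads: "Lubricate the itouch sure Probe with the conductive gel provided". Under Protocol 8.10.3, "the subjects will be instructed to use the device at home once per day for the 12-week period", with no rest days.

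**No vaginal product in the Vital Compact arm.** Appendix XI says that "the electrodes should lie on the quadriceps, hamstrings and gluteal muscles of both legs".

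**When the pads are worn.** Protocol 8.11.4 has subjects reminded before each visit to "start using their pre-packaged pads to complete the 24-hour pad collection 3 days prior to their appointment". Visit 4 lies within the treatment programme (8.11.3), and the device is handed back only at that visit (8.12). Baseline pads are worn before Visit 2 (8.9), and baseline assessments must be finished before randomisation (8.8).

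**How leakage is derived.** Under SAP 3.2, 24-hour leakage "is based on the increase in the weight of 8 pads (including packaging) after 24 hours of collection", averaged over the three periods. Nothing is deducted for material other than urine.

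**What contamination is controlled.** Protocol 8.9, 8.10.4 and 8.11.5 ask women to expel and record fluid after intercourse and to record menstruation on pad days. Gel is not mentioned.

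**The concern.** Key secondary endpoint 3 compares the change in 24-hour pad weight between arms as a superiority test meant to support labelling. If gel reaches the pad, it compares urine in one arm with urine plus gel in the other. The extra weight would appear only after treatment starts, so neither randomisation nor subtraction of baseline would remove it. It would understate the itouch reduction and so favour the sponsor's device.

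A false pass at step 3 would also open steps 4 to 11 of the hierarchy. The descriptive 24-hour dryness (<1.3 g) and >50% reduction rates at Weeks 4 and 12 would shift the same way. Under SAP 2.3.3, LOCF could carry an affected Week 4 value to Week 12. Once the pads have been weighed, gel cannot be separated from urine.

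**Working it through.** **The plan's own figure.** The only sample-size calculation is for the primary endpoint: 87 per group for 90% power. From the stated inputs (52% v 71%, margin 5%, one-sided 0.025) I get 84 per group with unpooled variance and 86 with pooled-null variance or Farrington–Manning, so the figure is broadly reproduced. The plan states no SD, effect size or power for endpoint 3.

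**Overlap.** SAP 1.6.2 makes randomisation Day 1, so Week 12 is about Day 85, and the window is ±7 days. SAP 3.7.2 expects itouch sessions equal to the visit day minus 1.

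| Week 12 visit day | Pad days | Expected itouch sessions |
|---|---|---|
| 78 | 75–77 | 77 |
| 85 | 82–84 | 84 |
| 92 | 89–91 | 91 |

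In each case an adherent itouch user has one session on every pad day, so averaging three days does not dilute the effect.

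**Direction.** Change is Week 12 minus baseline. If b grams per 24 hours reach the pad, b is added to the itouch Week 12 value and nothing to itouch baseline or to either Vital Compact value. The contrast moves by b towards Vital Compact.

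**Size on endpoint 3, tested alone.** The documents do not give b; I assume 0 to 3 g. The SDs come from the second-generation device pilot in Protocol 2.1 (19.41 g before, 5.16 g after). The correlation r is assumed to be 0.3 to 0.7.

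- SD of change = √(19.41² + 5.16² − 2r × 19.41 × 5.16) = 18.5 g (r = 0.3) to 16.2 g (r = 0.7).
- SE = SD × √(2/90) = 2.76 to 2.42 g.
- Chance of a significant result favouring Vital Compact when the devices are equal = 1 − Φ(1.96 − b/SE).

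| b (g/day) | Chance |
|---|---|
| 0 | 2.5% |
| 0.25 | 3.1–3.2% |
| 0.5 | 3.8–4.0% |
| 1 | 5.5–6.1% |
| 2 | 11–13% |
| 3 | 19–24% |

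A smaller SD would raise these figures: with an SD of 10 g and b = 1 g the chance is 9.9%.

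**24-hour dryness (descriptive).** Assume a lognormal with the pilot's post-treatment mean of 5.6 g and SD of 5.16 g. Then σ² = ln(1 + (5.16/5.6)²) = 0.615 and μ = ln 5.6 − σ²/2 = 1.415. P(X < 1.3) = 7.1%. With b = 0.5 g, P(X < 0.8) = 1.8%.

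**The case against.** **Transfer is an inference.** No passage says how much gel is used, how much remains after a session or how much reaches a pad. Steps 14 and 15 of the itouch instructions have the probe removed and washed, so some gel leaves with it. This stands: b may be near zero, and missed sessions add none. A reader might infer that the bias is established or always favours Vital Compact; the documents support only that it may.

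**The hierarchy limits the damage.** A reader might take 19–24% as the chance of a false label claim. It is not. Endpoint 3 supports a claim only after the primary endpoint and key secondaries 1 and 2 succeed. With equal devices, a common response rate of 46–71% and 90 per arm, the primary passes about 10–11% of the time. For example, at 52% the SE is √(2 × 0.52 × 0.48/90) = 0.0745, and 1 − Φ(1.96 − 0.05/0.0745) = 9.9%. Key secondary 1 is itself a two-sided 5% test. If the devices are equal on provocative leakage, the chance of a false endpoint 3 claim cannot exceed about 5%, whatever the gel weight. The stand-alone rates approach claim-level error only if Vital Compact truly wins on provocative leakage yet ties on 24-hour leakage.

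**The primary endpoint.** A reader might infer that the provocative pad is contaminated too. The documents do not support this. SAP 3.7.2 expects no itouch session on the visit day, and Appendix III gives the subject a fresh pad about an hour after she voids.

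**Other limits.** The 24-hour dryness and >50% reduction rates carry no formal test or labelling claim. The SDs come from a small pilot (14 subjects at Week 12) of an earlier device, not from itouch data. Only part of the diary and device record is visible, so a gel instruction could exist there. All of this stands, but none of it removes the one-arm exposure on the pad days.

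**Conclusion.** The point holds as a possible measurement bias, confined to one arm and to treatment, that the visible plan does not control. The documents establish the exposure, its timing and the direction of any effect, but not its size.

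On the stated assumptions (0 to 3 g per day, SD of change 16–18.5 g, 90 per arm, devices equal on 24-hour leakage), the stand-alone false-positive chance on endpoint 3 ranges from the nominal 2.5% to 19–24%. It is only about 3% at 0.25 g. The claim-level error is lower because of the gate.

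Key secondary 4 (within Vital Compact) and the Week 26 measures, taken after the device is returned, are not shown to be affected; nor is the primary endpoint. The case for acting rests on the low cost of prevention and on the protocol's own practice for intercourse fluid, not on a demonstrated effect.

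**What to change.** **Protocol 8.10.4 and 8.11.5.** Add an instruction parallel to the intercourse one: on pad-collection days, itouch users expel and wipe away residual gel after each session before the study pad is worn again, keeping any time off the pad as short as possible. The unblinded trainer should give it. Session time should go on the device record rather than the voiding diary, so that staff who review the diary stay blinded. Session frequency and duration do not change.

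**SAP 2.3.3.** Add a tipping-point sensitivity analysis for key secondary 3. Subtract a gel weight from itouch Week 12 values, starting at 0 g and flooring leakage at zero, and report the weight at which significance is lost. The floor matters: under the lognormal above, with no gel present, subtracting 2 g would make about 18% of itouch values negative, and 3 g about 34%.

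**Cost.** Slightly more instruction in one arm, one extra analysis, and no added visits or procedures. There are two downsides. A brief uncollected interval in the itouch arm could bias in the opposite direction, which is why time off the pad must be short. The subtraction is an assumption, not a measurement. The instruction must be in place before pads are collected.

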Step 14: Remove the itouch sure Probe from your vagina by grasping the probe flange and gently pulling outward. It is important that you do not pull from the wires, as it may become disconnected at the two-prong connection.

Step 15: Wash and thoroughly dry the itouch sure Probe before placing it and the itouch sure Control Unit into the storage pouch.

Note: As with any new exercise regimen, with the first few sessions your muscles may be a bit sore the next day.

Note: The next time you turn on the unit, it will default to the mode last used but at half strength. Thus, it may be beneficial for you to adjust the intensity to the desired setting for your next treatment session prior to turning off the itouch sure Pelvic Floor Exerciser.

iTOUCH SURE "SMART FEATURES"

itouch sure Pelvic Floor Exerciser is designed with state-of-the art electronic features including:

Controllable Stimulation

The strength of the stimulation is under your control. You can gradually increase or decrease the intensity whenever you want to make sure the stimulation always feels comfortable.

Easy Start - One Touch Memory

The itouch sure has intelligent memory that enables the unit to remember the last settings you used, and return to similar settings at your next use.

•Automatic Safety Shutoff

This feature automatically turns the device off after 20 minutes of use to protect the pelvic floor muscles from being overworked. If your physician recommends sessions that are longer than 20 minutes, you can adjust the device to override the safety shutoff and allow a longer session.

ITOUCH SURECONTROLS

To turn iTouch Sure ON: Press and hold the ON button for three seconds.
 When the unit turns on, you will hear a beep.

Memory Start

If you turned the unit off before completing the session, it will automatically start in the program you used last, at about 50% of the strength level you were using. This way you can adjust the strength comfortably for each new session.

Strength UP (▲) Button

To increase strength: Press and hold the Strength UP button until your desired strength is displayed on the screen.
 You may not feel any initial sensation, as it is a gentle increase of intensity.
 To increase the strength, press and release the button until you reach your required level. The strength will increase in 0.5 increments up to a maximum of 99.5.

Strength DOWN (▼) Button

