To decrease strength: Press and hold the Strength DOWN button until the desired strength is achieved. To decrease the strength, press and release the button until you reach your desired level.

Program (P) Button

iTouch Sure has four preset programs which appear as STRES, URGE, MIXD and TONE on the screen. You will be only using the STRES program in this study. The P Button is used to change the program. Please do not change the Program. If you accidentally change it you can get the STRES program back again by pressing the P button a few times.

Lock Button

The Lock button can be used to lock all the controls except for the strength down and OFF buttons. This way you won't accidentally change the settings while you use the unit, but you still have the ability to decrease the strength at any time. To lock the unit, press and hold down the Lock button for three seconds until LOCK is displayed on the screen. To unlock the unit, simply repeat.

(⌚) Time Selector Button

The itouch sure Pelvic Floor Exerciser counts down the minutes of your session. This countdown is displayed on the screen. When the count reaches zero, the unit will automatically turn off.

Each time you switch on the itouch sure, the time selector will be set at 20 minutes which is the treatment time for this study. Please do not change the timer setting.

To PAUSE the session - in case you need to suspend the treatment session and resume later - hold down the Time Selector button for three seconds. The display will read "PAUSE".

To return to the main screen, press any other key and you will return to the settings where you left off.

OFF (ⓧ) Button

To turn itouch sure OFF: Press the OFF button. You will hear a double beep.

NOTE: Always make sure the unit is OFF before removing the itouch sure Probe from your vagina.

SCREEN DISPLAYS

The screen lights up whenever a button is pressed.

LEADS ALARM

itouch sure monitors the contact between you, the Probe, and the itouch sure Control Unit. If either of these go outside of a standard range, while the strength is above 20.0, the unit will flash "LEADS", beep three times, and return strength to zero.

The most common causes are:

- Poor contact with your vaginal walls.
- A broken lead wire.
- A faulty connection at the USB port or at the dual probe connectors.

If the LEADS alarm sounds, make sure the wires are connected properly. If that doesn't solve the problem:

Change the position of the probe in the vagina; or

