Change your body position; or

Add lubrication to the itouch sure Probe so that it can make a better contact with the vaginal tissue.

If you have taken the above steps above and the alarm still shows, please refer to Troubleshooting section for further information.

Treatment

Please follow the instructions for use given to you by your study physician. The initial electrode fitting and the treatment session should be done under medical supervision by study staff.

Set the strength level to that prescribed by your study doctor. If you experience discomfort reset the intensity down one step. Don't "overdo" it early on. As long as you can feel the contractions, itouch sure is working properly. You can build up slowly over a number of sessions.

Your muscles may be sore the next day- the same reaction you would get with any new exercise - and you may need to stop using your itouch sure for a day or two until the soreness goes away, and then start again using a lower strength and shorter treatment time. As the pelvic floor muscles get stronger, you will be able to increase your strength level and time.

[figure not shown]
NOTE: itouch sure cycles between active stimulation and periods of rest. It is normal to feel the stimulation ramp down, stop briefly and then ramp back up again during treatment.

BATTERY USE

Inserting the Batteries

Open the battery cover:

Press down in centre of battery cover and slide the cover downwards in the direction of the raised arrows.

Insert the batteries in the direction shown inside the case. Make sure that the ribbon goes behind the batteries, which makes them easier to remove later. When the batteries are running low, a low battery indicator will show on the screen (battery symbol) and the display will begin to fade. The intensity of your workout, however, will stay the same until the battery runs out and the unit shuts off.

Battery removal and replacement:

When the batteries need to be changed the low battery sign, " BATT", will be displayed on the screen. To remove batteries, pull gently on the ribbon behind them. Remove batteries from your itouch sure unit if the unit is unlikely to be used for a long period.

Battery type:

ONLY use either AA alkaline batteries. . DO NOT mix batteries of different types. Do not try to recharge alkaline batteries. Properly dispose of used batteries, as batteries should not be disposed of with household waste.

Warning:

Keep batteries out of the reach of small children

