PRODUCT SPECIFICATIONS

Maximum Intensity	50V zero to peak.
Setting	0·100 in steps of 0.5
OC cutout	below 160 Ohm.
Constant current	160-470 Ohm 470-2000 Ohm constant voltage.
Channels	Single
Waveform	Asymmetrical rectangular
Max Pulse energy	*Total output limited to 25uC per pulse
Power	2 xAA Alkaline
Battery life	At least 15 hours at 50mA 300uS 50Hz
Adjustable Timer	10, 20, 30 45, 60, 90 min defaults to 20 min
Pause button	"Clock" key when running
Output plug	Fully shielded: touch-proof mini USB
Weight	90 gms without batteries
Dimensions	102 x 53 x 30 mm
Safety Classification	Internal power source.
Type BF	Designed for continuous use. No special moisture protection.
Environmental Operating:	Humidity: 20% - 65% RH
Storage Humidity:	10 to 90% RH Temperature range: 0°C to 55°C
Temperature range	0°C to 35°C

[figure not shown]
The electrical specifications are nominal and subject to variation from the listed values due to normal production tolerances.

PROGRAM SETTINGS

Program	Hz	Pulse Width (μS)	Ramp Up & Down (Sec)	Plateau (Sec)	Off (Sec)	Default Program Duration (Min)
STRESS	50	300	1	5	10	20
URGE	10	200	1	5	10	20
MIXED	20	250	2	5	10	20
TONE	35	250	2	3	6	20

Device Output Parameters and Waveform

The waveform below illustrates a typical output waveform from the iTouch Sure device:

Max Pulse Energy: 23 μ C

Use special precautions regarding EMC according to the information provided below.

Other portable and mobile RF communications equipment can affect performance.
Do not use when adjacent to or stacked with other electrical equipment.

Assistance

If you have any problems with your device please contact your study doctor whose contact details are on the Informed Consent form you received at the beginning of the study. For further assistance you may contact

Expedite Research, LLC [name]
[name]
Office [name]

These instructions for use were created specifically for study BMR 13 1001 by:

Bio-Medical Research Ltd. [name]

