1.3 STUDY DESIGN

This is a prospective, randomized, controlled, single-blind, multi-site clinical study to be conducted in the United States of America (USA) employing Neuromuscular Electrical Stimulation (NMES) to stimulate the pelvic floor muscles of women suffering from stress urinary incontinence.

Approximately one-hundred and eighty (180) female subjects diagnosed with stress urinary incontinence will be enrolled in this study. All subjects who are considered eligible to participate in the clinical study and give consent will be randomised to complete either a 12-week treatment programme with the Vital Compact device or a 12-week treatment programme with the itouch Sure Pelvic Floor Exerciser. The 12-week treatment programme will be completed by the subjects at home with treatment with the device in accordance with the device Instructions for Use. Subjects randomized to the Vital Compact device will be instructed to use the device at home once per day, in a therapeutic position, for five days each week with two rest days taken within a 7 day week period, for the 12-week period; each treatment cycle is fixed at 30 minutes and the device will alert the subject when the cycle is completed. Subjects randomized to the itouch Sure Pelvic Floor Exerciser will be instructed to use the device at home once per day for the 12-week period; each treatment cycle is fixed at 20 minutes and the device will alert the subject when the cycle is completed.

Subjects included in the clinical study will be evaluated at screening, on enrolment into the study (baseline) and during the 12-week treatment programme at 4 and 12 weeks. A telephone call will be made at 1 week to check on the subject's progress. In addition, subjects will be evaluated at 26 weeks following their commencement of the treatment.

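### The study-specific itouch manual conflicts with itself, the protocol and the SAP on session length and daily use, and the SAP's use percentages count sessions rather than minutes

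*Protocol*

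**What the plan says.** Three places give one schedule for the comparator. Protocol 8.10.3 prescribes once-daily use for 12 weeks and says: "Each treatment cycle is fixed at 20 minutes and the device will alert the subject when the cycle is completed". SAP 1.3 repeats it: "each treatment cycle is fixed at 20 minutes and the device will alert the subject when the cycle is completed". The label text in Protocol 7.2.1 gives 20 minutes, 7 days a week.

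Protocol 7.2 says the device is used according to the Instructions for Use supplied for the study. That manual is Appendix XII, and its last page says it was written for this trial.

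The manual first agrees with the schedule. Step 12 reads: "The length of each session has been set at 20 minutes. Please do not change the preset time". The Time Selector entry repeats: "Please do not change the timer setting".

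It then departs from it:

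- Its Treatment section says that muscles may be sore and that the user may need to stop for a day or two, "then start again using a lower strength and shorter treatment time".
- The next sentence adds: "As the pelvic floor muscles get stronger, you will be able to increase your strength level and time".
- Its Automatic Safety Shutoff entry says that, where the physician recommends more than 20 minutes, "you can adjust the device to override the safety shutoff and allow a longer session".
- The product specification lists the timer as "10, 20, 30 45, 60, 90 min defaults to 20 min".

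**The concern.** The manual is the document a participant uses at home, and the protocol makes it govern use. A woman with soreness reads a request to leave the timer alone and use the device daily, and also advice to skip days and shorten sessions. She cannot do both, and the site has no stated rule for classifying what she did.

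The comparator arm matters most here because the primary test is non-inferiority to itouch with a 5-point margin (Protocol 10.3.3). Reduced comparator exposure could make the new device look better than it is. The Vital Compact manual (Appendix XI) lets a session be split but keeps a cumulative 30 minutes per day. It contains no advice to restart with shorter sessions.

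The per-protocol set in SAP 2.1 requires that compliance criteria were met and that there were no significant deviations. Neither document says where a shortened session or a manual-advised rest day falls.

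**Working it through.** **1. The instructions side by side**

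| Source | Session length | Daily use |
|---|---|---|
| Protocol 8.10.3, SAP 1.3 | 20 min, fixed | Once per day |
| Protocol 7.2.1 (label) | 20 min | 7 days a week |
| Appendix XII, Step 12 and Time Selector | 20 min, do not change | – |
| Appendix XII, Treatment | Shorter after soreness, may increase later; no lengths given | A day or two without use after soreness |
| Appendix XII, Safety Shutoff | Longer if the physician recommends it; no limit given | – |

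For a user without soreness and without a physician's recommendation, the rows can be reconciled. For a user with soreness they cannot.

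**2. The plan's own exposure figure**

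SAP 3.7.3 prescribes 12 × 7 = 84 itouch sessions, which reproduces. At 20 minutes each, that is 84 × 20 = 1,680 minutes.

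**3. How the SAP scores departures**

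Percent of target use = sessions used / sessions prescribed × 100. Percent of actual use (SAP 3.7.2) has the same numerator. Its itouch denominator is the relative day of the Week 12 visit minus 1, which is also 84 if that visit falls on Day 85 (assumed here).

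- *Shortened sessions.* The only timer setting below 20 minutes is 10. In the extreme case of every session at 10 minutes (an assumption, used only as a bound), exposure is 84 × 10 = 840 minutes, and 840 / 1,680 = 50%. Target use is 84 / 84 = 100%.
- *Rest days.* Two days off with all other sessions at full length give 82 × 20 = 1,640 minutes, and 1,640 / 1,680 = 97.6%. Target use is 82 / 84 = 97.6%. One day off gives 83 / 84 = 98.8%.

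So the woman with 840 minutes scores higher than the woman with 1,640. Average duration per session (SAP 2.4.1) would separate them, at 10 against 20 minutes.

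**4. Direction of any effect on the primary result**

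The planned rates are 71% for Vital Compact and 52% for itouch (Protocol 10.2). The planned difference is 71 − 52 = 19 points, which is 19 + 5 = 24 points from the margin. The stated sample size reproduces with the pooled variance. With a mean rate of (0.71 + 0.52) / 2 = 0.615:

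2 × 0.615 × 0.385 × (1.960 + 1.282)² / 0.24² = 86.4, so 87 per group.

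The manual's wording does not affect that calculation. If shorter use lowered the itouch rate by x points, the difference would become 19 + x, further from the margin. If longer use raised it by x, the difference would become 19 − x. Neither document relates session length to response, so x and its net sign are unknown.

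**The case against.** Much of the case on the other side stands.

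- **Departures are conditional.** Soreness may occur, and the user may need to pause. The sentence on increasing time can be read as a return to 20 minutes. Longer sessions need a physician's recommendation.
- **Departures take a deliberate act.** The manual says the timer is set to 20 minutes at each switch-on, so a changed setting does not persist. A lock function is available.
- **Duration is recorded.** The daily record captures it (Protocol 7.7), unblinded staff record device data on it (8.11.5), and SAP 2.4.1 summarises it. The Week 1 call (8.11.2) checks use against the instructions, although these contain the conflict.
- **The other arm has some flexibility.** The Vital Compact manual lets the prescribing clinician change its daily session limit and lets users switch off at any time. Only the explicit advice to restart with shorter sessions is particular to itouch.
- **Classification is still open.** SAP 2.1 allows the per-protocol criteria to be completed before unblinding.

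A reader might go further in four ways that the documents do not support:

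- *That the comparator was under-dosed.* The text shows that the instructions do not fix the dose. It does not show that any woman's dose varied.
- *That the effect could consume the margin.* Assuming that 20% of itouch women shorten sessions and lose 25 points of response gives 0.20 × 25 = 5 points, but both inputs are invented. A 25-point fall from 52% would remove 25 / 52 = 48% of responders.
- *That women are directed to 90-minute sessions.* That is a hardware setting. No instruction directs it.
- *That shortening would pull the arms together.* Under the planned rates, a lower itouch response widens the gap.

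What survives is the contradiction itself, and two use percentages that do not register session length.

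**Conclusion.** The point holds as an inconsistency in participant-facing instructions for the comparator. Appendix XII cannot be followed as written by a woman with soreness, and it disagrees with Protocol 8.10.3, the label and SAP 1.3 on both session length and daily use.

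On measurement, both SAP use percentages score a shortened session as full and a rest day taken on the manual's advice as non-use. The 50% exposure figure is a bound that assumes the 10-minute setting throughout. It is not an estimate. Average session duration makes shortening partly visible.

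Reduced comparator exposure could favour the new device, and increased exposure would act the other way. The size and net direction of any effect on the primary endpoint cannot be derived from the documents. The reason to act is that the conflict concerns comparator exposure in a non-inferiority trial and is cheap to remove, not that a bias has been shown.

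**What to change.** - Reconcile the label text (Protocol 7.2.1), Protocol 8.10.3, SAP 1.3 and the Appendix XII entries (Step 12, Time Selector, Safety Shutoff, Treatment) so that one consistent instruction on session length and missed days applies. The sponsor and investigators decide which rule stands.
- State before unblinding, with the per-protocol criteria in SAP 2.1, whether a departure from that instruction is permitted use or a protocol deviation. Cover both shortened or lengthened sessions and skipped days.

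The cost is a reprint of the study manual, IRB notification and a line in site training.
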